7.5.5.5. Global Assessment Scales

7.5.5.5.1. Patient Global Impression of Severity

Patients will be asked to rate their overall severity of symptoms in the PGIS ([Appendix G](#)) at all study assessment time points specified in the Schedule of Assessments ([Appendix A](#)). Patients will be asked to choose the response that best describes the severity of the NTM lung disease symptoms over the past 7 days. The PGIS uses a 5-point Likert scale (None [0], Mild [1], Moderate [2], Severe [3], and Very Severe [4]) ([Yalcin, 2003](#)) ([FDA, 2018](#)).

7.5.5.5.2. Patient Global Impression of Change

Patients will be asked to rate the overall change in symptoms in the PGIC ([Appendix G](#)) at all study assessment time points specified in the Schedule of Assessments ([Appendix A](#)). Patients will be asked to choose the response that best describes the overall change in the severity of the NTM lung disease symptoms since starting the study. The PGIC uses a 5-point Likert scale (Much Better [0], A Little Better [1], No Change [2], A Little Worse [3], or Much Worse [4]) ([Yalcin, 2003](#); [FDA, 2018](#)).

7.5.5.5.3. Clinician Global Impression of Severity

Investigators will be asked to rate their impression of the overall severity of the patient's symptoms in the CGIS ([Appendix G](#)) at all study assessment time points specified in the Schedule of Assessments ([Appendix A](#)). The Investigators will be asked to choose the response that best describes the severity of the patient's NTM lung disease symptoms ([Busner, 2007](#)). The CGIS uses responses of None (0), Mild (1), Moderate (2), Severe (3), or Very Severe (4).

7.5.5.5.4. Clinician Global Impression of Change

Investigators will be asked to rate their impression of the overall change in symptoms in the CGIC ([Appendix G](#)) at all study assessment time points specified in the Schedule of Assessments ([Appendix A](#)). Investigators will be asked to choose the response that best describes the severity of the patient's NTM lung disease symptoms compared to the baseline ([Busner, 2007](#)). The CGIC uses responses of Much Better (0), A Little Better (1), No Change (2), A Little Worse (3), or Much Worse (4).

7.5.5.6. Meaningful Change Question

After every time the PGIC is completed, the patient will answer a question to gauge whether the change (better, worse, same) in their symptoms is meaningful to them ([Appendix H](#)).

7.5.6. Qualitative Embedded Interviews

A subset of up to 40 patients in the Phase 2 part of the study will participate in an optional qualitative embedded interview to share their experience in the study. The final sample size will depend on site recruitment totals and participant willingness to complete the optional interview.

Patients who are enrolled in the Phase 2 part of the study must meet the following criteria to be considered eligible to participate in an interview:

- Complete their Month 6 Visit or receive at least 8 weeks of treatment if study drug was prematurely discontinued prior to Month 6.
- Be able to speak, read, and understand English or other approved language well enough (based on site staff judgment) to complete an interview via telephone or web conference and be willing to have their interview audio recorded.
- Not have issues with cognition or hearing, or other issues that would make it difficult (based on site staff judgment) to participate in an interview via telephone or web conference.

Evidera, a CRO, has been contracted to conduct the interviews. A site staff member will share patient contact information with Evidera via a secure location. Evidera staff will contact participants directly to schedule and conduct the interviews. All interviews will be conducted via telephone or web-based teleconference, based on participant preference and capabilities.

Interviews will be conducted in English or other approved language and will last approximately 30 to 45 minutes. The interview will take place within 2 weeks (up to 4 weeks maximum) after the Month 6 Visit or within 1 week (up to 3 weeks maximum) after the EOT Visit (if the EOT Visit occurs within the first 6 months and if the patient has completed at least 8 weeks of treatment).

During the interviews, patients will be asked to discuss how each of their symptoms improved, worsened, or remained the same, and whether those changes were meaningful, using the MACrO₂ PRO to anchor the discussion. Interviewers will use an open-ended, semi-structured interview guide to lead the discussion. All interviews will be audio-recorded and transcribed for analyses.

It is possible that Phase 2 patients will report AEs during the course of their qualitative embedded interview. All Evidera researchers conducting interviews will undergo training to listen for suspected AEs. The Evidera researchers will not evaluate the suspected AE but rather will document the patient's report and alert the site study team within 24 hours for further evaluation, per study procedures.

Interviews will qualitatively evaluate the proposed symptom-based clinical response definition within the context of the clinical study. Results from the embedded interviews will be used to inform or confirm the symptom-based clinical response definition in the analysis plan for the Phase 3 endpoints. All interviewers will be blind to the patient's treatment allocation.

7.6. Randomization

Patients will be randomized using an IRT system per Sections 5.3 and 5.5.2.1.

7.7. Study Drug Administration

Study drug will be administered per Section 5.5.2.

7.8. Adverse Events Assessment

AEs will be assessed per Section 7.9.

7.9. Safety Monitoring and Reporting

See Section 7.5 and Appendix A for assessments and procedures related to safety, including vital signs, laboratory tests (eg, chemistry, hematology, urinalysis), ECGs, and AEs.

7.9.1. Adverse Events

An AE is defined as any untoward medical occurrence in a clinical investigation patient administered a pharmaceutical product, which does not necessarily have a causal relationship with this treatment. An AE can therefore be any unfavorable and/or unintended sign (including an abnormal laboratory finding), symptom, or disease temporally associated with the use of a drug whether or not related to the drug.

All AEs, including observed or volunteered problems, complaints, or symptoms, are to be recorded in the appropriate eCRF. AEs will be collected from the time of the first dose of study drug through EOT.

SAEs will be collected from the time of informed consent through LFU.

Any medical condition or signs/symptoms already present at the time of first dose of study drug should be recorded as medical history and not be reported as an AE unless the medical condition or signs/symptoms present at baseline changes in severity, frequency, or seriousness at any time after administration of the first dose of study drug. In this case, it should be reported as an AE.

Patients should be instructed to report any AE that they experience to the Investigator, whether or not they think the event is due to study drug. Beginning with the date of the first dose of study drug, Investigators should make an assessment for AEs at each visit and record the event in the appropriate AE eCRF. If an observed or reported sign or symptom is part of the symptom-based clinical endpoint (eg, a worsening symptom associated with the underlying MAC lung infection), it should *not* be captured as an AE, with the exception of events that meet criteria for SAE (eg, deaths, hospitalizations); see Section 7.9.2.

Wherever possible, a specific disease or syndrome rather than individual associated signs and symptoms should be identified by the Investigator and recorded in the eCRF. However, if an observed or reported sign or symptom is not considered a component of a specific disease or syndrome by the Investigator, it should be recorded as a separate AE in the eCRF. Additionally, the condition that led to a medical or surgical procedure (eg, surgery, endoscopy, tooth extraction, or transfusion) should be recorded as an AE, not the procedure itself.

Clinically significant abnormal laboratory or other examination (eg, ECG) findings that are detected during the study or are present at the time of first dose of study drug and significantly worsen during the study should be reported as TEAEs, if they cannot be ascribed to a specific medical condition or are associated with a specific underlying disease (eg, isolated elevation of ALT or AST that is not associated with a clear diagnosis or specific hepatic condition). Otherwise, abnormal laboratory values should be captured collectively under a unified disease or diagnosis (ie, a single TEAE disease term), rather than separate TEAEs for each individual laboratory abnormality. Clinically significant laboratory abnormalities or other abnormal clinical findings (eg, ECG abnormalities) include, but are not limited to, events that require intervention or if an action is taken with the study drug as a result of the abnormality. Abnormal test results that are determined to be an error should not be reported as an AE. The Investigator will exercise their medical and scientific judgment in deciding whether an abnormal laboratory finding or other abnormal assessment is clinically significant.

All clinically significant abnormal laboratory values occurring during the clinical study must be followed until repeat tests return to normal, stabilize, or are no longer clinically significant. Such laboratory values will be captured as unscheduled assessments in the electronic data capture (EDC) system if they are collected outside of protocol-defined study visits (eg, after LFU).

7.9.1.1. Assessment of Adverse Events by the Investigator

7.9.1.1.1. Assessment of Severity

Investigators should use CTCAE version 5.0 ([NIH, 2017](#)) for guidance in determining the severity of TEAEs. For those AE terms not listed in the CTCAE, the following grading system should be used:

- CTCAE Grade 1: Mild; asymptomatic or mild symptoms; clinical or diagnostic observations only; intervention not indicated
- CTCAE Grade 2: Moderate; minimal local or noninvasive intervention indicated; limiting age-appropriate activities of daily living
- CTCAE Grade 3: Severe or medically significant but not immediately life-threatening; hospitalization or prolongation of hospitalization indicated; disabling; limiting self-care activities of daily living
- CTCAE Grade 4: Life threatening consequences; urgent intervention indicated
- CTCAE Grade 5: Death related to AE

7.9.1.1.2. Causality Assessment

The relationship of an AE to the administration of the study drug is to be assessed according to the following definitions:

- Definitely related: A reaction that follows a reasonable temporal sequence from administration of study drug, follows a known or expected response pattern to the study drug, disappears or decreases on cessation or reduction in study drug dose, and/or it reappears or worsens when the study drug is administered.

- Probably related: A reaction that follows a reasonable temporal sequence from administration of study drug, follows a known or expected response pattern to the study drug, and/or that could not be reasonably explained by other factors such as underlying disease, complications, concomitant drugs, or concurrent treatments.
- Possibly related: A reaction that follows a reasonable temporal sequence from administration of study drug and follows a known or expected response pattern to the study drug, but could have reasonably been produced by a number of other factors including underlying disease, complications, concomitant drugs, or concurrent treatments.
- Not related: A reaction for which sufficient data exist to indicate that the etiology is unrelated to the study drug. This definition implies there is not a reasonable possibility of a causal relationship between the event and the study drug, meaning that there are facts (ie, evidence) or arguments to suggest there is not a causal relationship.

The following factors should also be considered:

- The temporal sequence from study drug administration: The event should occur after the study drug is given. The length of time from study drug exposure to event should be evaluated in the clinical context of the event.
- Underlying, concomitant, intercurrent diseases: Each report should be evaluated in the context of the natural history and course of the disease being treated and any other disease the patient may have.
- Concomitant drug: The other drugs the patient is taking or the treatment the patient receives should be examined to determine whether any of them might be recognized to cause the event in question.
- Known response pattern for this class of study drug: Clinical and/or preclinical data may indicate whether a particular response is likely to be a class effect.
- Exposure to physical and/or mental stresses: The exposure to stress might induce adverse changes in the recipient and provide a logical and better explanation for the event.
- The pharmacology and PK of the study drug: The known pharmacologic properties (absorption, distribution, metabolism, and excretion) of the study drug should be considered.

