7.9.5. Expedited Reporting

The Sponsor/designee will report all relevant information about Suspected Unexpected Serious Adverse Reactions (SUSARs) that are fatal or life-threatening as soon as possible to the FDA, applicable competent authorities in all the countries and Member States concerned, and to the IECs, and in any case no later than 7 days after knowledge by the Sponsor/designee of such a case. Relevant follow-up information will subsequently be communicated within an additional 8 days.

All other SUSARs will be reported to the FDA, applicable competent authorities concerned, and to the IECs concerned as soon as possible but within a maximum of 15 days of first knowledge by the Sponsor/designee.

The Sponsor/designee will also report any additional expedited safety reports required in accordance with the timelines outlined in country-specific legislation.

The Sponsor/designee will also inform all Investigators as required per local regulation.

The requirements above refer to the requirements relating to IMP.

Expedited reporting of SUSARs related to non-investigational medicinal products (NIMPs) (and any other NIMPs) is not required. Listings of cases related to NIMPs will be included in the Development Safety Update Report.

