3.5.1 Treatment-emergent Adverse Events (TEAEs)

An AE is defined as any untoward medical occurrence in a clinical investigation patient administered a pharmaceutical product, which does not necessarily have a causal relationship with this treatment. An AE can therefore be any unfavorable and/or unintended sign (including an abnormal laboratory finding), symptom, or disease temporally associated with the use of an investigational medicinal product, whether or not related to the investigational medicinal product (IMP), whether or not related to the IMP. All AEs, including observed or volunteered problems, complaints, or symptoms, are to be recorded on the appropriate eCRF. SAEs occurring from the time of informed consent through LFU will be collected. For non-serious AEs, TEAEs are defined as AEs that started from the time of the first dose of study drug through EOT; for serious AEs, TEAEs are defined as SAEs that started from the time of the first dose of study drug through LFU.

Investigators will monitor each patient for clinical and laboratory evidence for pre-defined AEs of special interest (AESIs) through LFU.

For this study, gastrointestinal intolerance, anemia, and (added prior to the Phase 3 analysis only) pneumonitis are considered AESIs. During the course of the study, additional AESIs may be identified by the Sponsor, and will be documented to support safety analyses at each analysis time point. A list of preferred terms to be included as AESIs by category will be finalized by the Sponsor prior to database lock and unblinding of each planned analysis.

AESIs related to gastrointestinal intolerance include, but are not limited to:

- *C. difficile* colitis

- Pseudomembranous colitis
- *C. difficile* test positive
- Diarrhea
- Nausea
- Vomiting

AESIs related to anemia include, but are not limited to:

- Anemia
- Aplastic anemia
- Coombs negative hemolytic anemia
- Coombs positive hemolytic anemia
- Hematocrit decreased
- Hemoglobin decreased
- Hemolysis
- Hemolytic anemia
- Intravascular hemolysis
- RBC decreased

AESIs related to pneumonitis (for Phase 3 only) included, but are not limited to:

- Pneumonitis
- Hypersensitivity pneumonitis
- Interstitial lung disease
- Pulmonary toxicity

An overview of AEs will be provided including counts and percentages of patients (and event counts) with the following:

- Any TEAEs (overall and by maximum severity)

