- Any study drug related (definitely related, probably related, and possibly related) TEAEs (overall and by maximum severity)
- Any treatment-emergent AESIs (overall and by maximum severity, as well as by specific AESI category as described above)
- Any serious AEs (SAEs)
- Any TEAEs related to COVID-19
- Any treatment-emergent SAEs
- Any study drug related treatment-emergent SAEs
- Any TEAEs leading to premature discontinuation of study drug
- Any TEAEs leading to study drug interruption
- Any TEAEs of Grade 3 anemia or worse leading to study drug interruption
- Any AEs leading to death

Counts and percentages of patients will also be presented by SOC (or AESI category) and PT for each of the categories listed in the overview. Summaries of all TEAEs, all study drug related TEAEs, and all SAEs by decreasing frequency of PT for epetraborole will also be provided by treatment and overall. Based on version 25.0 or later of MedDRA, AEs reported due to COVID-19 will be appropriately coded in the listings and identifiable in the summary tables and listings by SOC and PT.

AE summaries will include the number of patients with a given AE, as well as the number of AEs themselves.

For all summaries, patients will be counted once for each AE category, SOC, or individual AE PT. For the summaries by severity grade, every patient will be counted once for each AE at the highest severity.

An overview of AEs in the format described above will be provided for key subgroups of interest, including age category, sex, geographic region and country, baseline creatinine clearance category (<60 mL/min, ≥60 mL/min to <90 mL/min, or ≥90 mL/min), and baseline BMI category (<18.5 vs ≥18.5 kg/m²).

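### The possibly-related category presupposes a known reaction pattern, so an unexpected event with a competing cause fits no related category and can be left out of the drug-related tables

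*Protocol*

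**What the plan says.** Protocol 7.9.1.1.2 gives investigators four categories.

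- *Definitely related*: plausible timing, a known or expected pattern, and an event that "disappears or decreases on cessation or reduction in study drug dose, and/or it reappears or worsens when the study drug is administered".
- *Probably related*: plausible timing, a known or expected pattern, "and/or that could not be reasonably explained by other factors such as underlying disease, complications, concomitant drugs, or concurrent treatments".
- *Possibly related*: plausible timing and an event that "follows a known or expected response pattern to the study drug, but could have reasonably been produced by a number of other factors".
- *Not related*: "A reaction for which sufficient data exist to indicate that the etiology is unrelated to the study drug". The text then explains that no reasonable chance of a causal link remains, and it admits reasoned argument as well as factual evidence.

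SAP 3.1.4 says causality may not be missing and that blanks are queried. SAP 3.5.1 tabulates "Any study drug related (definitely related, probably related, and possibly related) TEAEs", with a matching row for treatment-emergent SAEs and exposure-adjusted summaries.

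For SAEs, Protocol 7.9.3.1 requires all of them to be reported within 24 hours through LFU. After LFU it requires only those the investigator considers related. Protocol 7.9.2 adds sponsor review and an ultimate causality determination that takes ICH and FDA guidelines into account. Protocol 7.9.5 makes the sponsor or designee responsible for reporting "Suspected Unexpected Serious Adverse Reactions (SUSARs) that are fatal or life-threatening", and other SUSARs on a longer timeline.

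**The concern.** A possibly-related category normally catches events for which the drug cannot be ruled out. Here it is open only to reactions already recognised for the drug, so a new kind of reaction with any rival explanation has no natural place.

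Rival explanations are built into this population. Every patient has treatment-refractory lung disease and takes a background regimen of at least 2 antimycobacterial agents (Protocol 4.1 and 5.7.1). The known pattern is also short: Protocol 5.2 describes the study dosage as given for up to 28 days, whereas treatment here may last up to 16 months. A late toxicity could not yet be an expected pattern.

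Pneumonitis illustrates the exposed type of event. Protocol 7.9.1.2 names only GI intolerance and anemia as AESIs, while SAP 3.5.1 says "gastrointestinal intolerance, anemia, and (added prior to the Phase 3 analysis only) pneumonitis are considered AESIs". At stake are the tables restricted to drug-related events and the reporting of SAEs after LFU.

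**Working it through.** There is no figure in the plan to reproduce, so the check is logical. Code each event as follows: T = plausible timing; K = known or expected pattern; O = another factor could explain it; D = positive dechallenge; R = positive rechallenge; E = facts or arguments against the drug are accepted.

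The and/or wording is ambiguous, so several readings were tried.

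- *Definitely*: (A) T and K and (D or R); (B) (T and K and D) or R; (C) T and ((K and D) or R).
- *Probably*: (1) T and K and not O; (2) T and (K or not O).
- *Possibly*: T and K and O.
- *Not related*: E.

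This gives 3 × 2 = 6 combinations of readings.

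**The gap event: T = 1, K = 0, O = 1.**

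- Definitely: A = 0; B = R; C = R.
- Probably: reading 1 = 0, since K = 0; reading 2 = 0, since neither K nor not-O holds.
- Possibly: 0, since K = 0.
- Not related: E.

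| Rechallenge | Facts or arguments against the drug | Category met |
|---|---|---|
| Not positive | None | None, under all 6 combinations, whatever the dechallenge result |
| Positive | None | None under A; definitely related under B or C |
| Not positive | Accepted | Not related only |

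One looser reading lies outside the six: in *probably*, timing alone might suffice. The event would then be rated probably related although it fails the weaker category, as would every event with plausible timing. That reading does not give a usable scale.

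**Neighbouring events.** With K = 0 and O = 0, reading 2 gives probably related and reading 1 does not. With K = 1 and O = 1, reading 2 meets both probably and possibly. The and/or therefore needs settling in any case.

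**From rating to tables.** A value is compulsory (SAP 3.1.4). Without rechallenge, the only category the gap event can reach on the wording is *not related*, by way of an argument such as the underlying lung disease. *Not related* is not counted as drug-related (SAP 3.5.1).

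**From rating to reporting.** Through LFU, reporting of an SAE does not depend on the rating. After LFU it does.

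**With the known-pattern condition removed.** Possibly becomes T and O, which is 1 for the gap event whatever K is.

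**The case against.** The strongest reply is that little in safety surveillance rests on this field. TEAEs are tabulated by SOC and PT regardless of relationship (Protocol 8.2.2). SAEs, AESIs, deaths, discontinuations and interruptions are too (SAP 3.5.1). The trial is randomized and blinded, and a DSMB sees unblinded safety data (Protocol 8.3.2). All of this stands, and it limits the point to relatedness-specific outputs.

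A reader might infer that unexpected reactions drop out of the SUSAR pathway. The documents do not support that through LFU: all SAEs reach the safety function, and the final causality determination is not stated to be bound by the four categories. Loss there is a risk only if the investigator's category is carried forward unchanged. The protocol describes no such second review for non-serious events.

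A reader might also infer that *not related* demands proof against the drug, or that gap events will certainly end up there. The definition accepts arguments, which lowers the bar. It also excludes any event for which a reasonable possibility of causation remains, so a careful investigator may refuse it and tick *possibly* despite the wording. The direction is an inference.

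Finally, a reader might take the late addition of pneumonitis as evidence of a missed signal. Nothing shows how any pneumonitis event was rated, and the protocol allows AESIs to be added. AESI tables do not depend on causality.

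The timing objection is partly right: the sponsor terminated the trial on 08 August 2024 (SAP 1), so a protocol edit alone would not change ratings already recorded.

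**Conclusion.** The point holds in a limited form and should be corrected. As written, an unexpected event with plausible timing, a competing cause and no positive rechallenge cannot be rated possibly related, and it meets *not related* only if facts or arguments against the drug are accepted. It can therefore be missing from the drug-related TEAE and SAE tables and, after LFU, from SAE reporting. The all-causality comparison between arms is untouched.

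No size can be stated. That no gap event qualifies as possibly related follows from the definition and is not an estimate of how many events are affected. Events with a known pattern are not excluded by this condition.

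The conclusion assumes that investigators apply the definitions as written and that the drug-related tables use the investigator's rating; neither document says which assessment feeds them. The value of a query now also assumes that Phase 3 is still blinded, as SAP version 3.0 implies (SAP 1 and 3.4).

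**What to change.** In Protocol 7.9.1.1.2:

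- Redefine *possibly related* as reasonable timing, whether or not the event matches a known pattern, where other factors could also have produced it.
- Clarify the and/or in *probably related*.
- State that an event not meeting *not related* is rated at least *possibly related*.
- State how the sponsor's SAE determination relates to the investigator's category, and in SAP 3.5.1 which of the two feeds the drug-related tables.

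Before the Phase 3 lock, query causality on blinded data for SAEs and pneumonitis-type AESIs rated not related despite plausible timing, and ask for re-rating under the corrected definition. Include events where a competing cause is recorded only as possible. A query confined to events with no recorded alternative would miss the gap, which consists of events that have one. If the lock has already passed, any re-rating should be labelled post hoc.

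The cost is a short text change, a site memo and a limited query. The number of events counted as drug-related may rise in both arms, by an amount the documents do not allow anyone to predict.
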